Clinical Trials (IMMPACT) consensus statement. All data collection will be through standard UCSD EPIC notes and patient interviews in-person during hospitalization or *via* a telephone call for outpatients. Postoperatively, surgical endpoints will be recorded such as surgical duration. All pain scores will be measured using the Numeric Rating Scale (0: no pain, 10: worst imaginable pain). On Days 35 and 70, amputees will be asked if they would want to continue using the device; and on Day 28 surgical patients will be asked if they would want to use the device if they were to have the same surgery in the future? For Phase II surgical participants, Days 21 and 28 will be excluded due to the shorter treatment period (8 days) of this device relative to that used in Phase I. At all time points for amputees, phantom and residual limb pain will be distinguished and recorded separately.

	Surgical Patients Postoperative Days								Amputees Post-Application Days						
Time Point:															
	1	2	3	7	14	21	28	180	0	2	4	7	21	28	35
Opioid consumption	•	•	•	•	•	•	•	•	•	•	•	•	•	•	•
Average Pain [NRS]	•	•	•	•	•	•	•	•	•	•	•	•	•	•	•
Worst Pain [NRS]	•	•	•	•	•	•	•	•	•	•	•	•	•	•	•
Brief Pain Inventory,				_	_	-	•							•	
Short Form				•	•	•	•		•					•	•
Patient Global												_	•	•	
Impression Change										•	•	•	•	•	•
Sleep disturbances	•	•	•		•	•	•		•	•	•			•	
(#) previous night	•				-					-	-				-
Passive flexion					•										
(knees and hips)															

Summary of post-enrollment assessments (color added for clarity)

Primary end points: This is an exploratory pilot study to assist in planning subsequent definitive trials and we therefore have no data analysis plan. For surgical patients, the two outcomes of primary interest will be (1) the "average" and "worst" pain measured with the Numeric Rating Scale (included in the Brief Pain Inventory pain domain), and (2) opioid consumption within the first 7 postoperative days. For amputees, the outcome measures of primary interest will be (1) the change in "average" residual and phantom limb pain scores between baseline and Day 28 of the initial treatment, as well as (2) the Patient Global Impression of Change on Day 28 of the initial treatment.

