For Phase II, there will be a total of 70 surgical participants, and these patients will be analyzed separately from Phase I surgical and amputation patients. Sample size calculations are based upon the hypothesis that pulsed electromagnetic field therapy decreases **pain** in the 7 days following moderate-to-severely painful surgical procedures. The primary outcome calculated as follows: for each participant all of the "average" and "worst" daily pain scores collected within the first 7 postoperative days will be summed. We will use these summed scores from participants having cholecystectomy (n=30), and hip and knee arthroplasty (n=40) to estimate a probable sample size.

We will consider a 33% reduction in pain scores to be the minimal clinically important difference [Farrar et al. J Pain Symptom Management 2003; 25: 406-11]. Based on values from patients receiving sham in Phase I, we anticipate the sham group to have an anticipated mean (SD) of 23.9 (12.3). Assuming a two-sided type I error protection of 0.05 and a power of 0.80, approximately 25 patients in each group are required (ClinCalc.com, accessed 2/23/23). To allow for a higher degree of variability than anticipated we will enroll a total of 70 participants in Phase II: cholecystectomy (n=30), and hip and knee arthroplasty (n=40).

Continuous, normally-distributed data will be reported as mean ± standard deviation. Nonparametric continuous or categorical data will be reported as median [10th-90th percentiles] or precents, as appropriate. Comparisons of independent samples will be performed using Student's t-test for parametric continuous variables or Mann-Whitney U test for nonparametric or categorical variables. The Chi Square test and Fisher's Exact test will be used for differences in proportions, as appropriate. P<0.05 will be considered statistically significant for the primary outcome. Results of comparisons in secondary outcomes will be interpreted as suggestive, requiring confirmation in a future trial before considering them as definitive.

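### The Phase II primary outcome is a raw sum of whatever pain scores were collected, so a missed contact counts as zero pain unless a rule is added

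*Combined protocol and SAP*

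**What the plan says.** All of this is in section 9 (Research Design and Methods) of the combined protocol and SAP.

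- **Outcome.** For Phase II, each participant's average and worst "daily pain scores collected within the first 7 postoperative days will be summed".
- **Scale.** "All pain scores will be measured using the Numeric Rating Scale (0: no pain, 10: worst imaginable pain".
- **Schedule.** The table captioned "Summary of post-enrollment assessments (color added for clarity" has surgical pain contacts on Days 1, 2, 3 and 7 within the first week and none on Days 4 to 6. A complete sum is therefore 4 contacts x 2 scores = 8 scores, with a range of 0 to 80.
- **Collection.** "All data collection will be through standard UCSD EPIC notes and patient interviews in-person during hospitalization", and by telephone once participants are outpatients.
- **Planning values.** "We will consider a 33% reduction in pain scores to be the minimal clinically important difference". The sham mean of 23.9 (SD 12.3) is "Based on values from patients receiving sham in Phase I".
- **Analysis.** Student's "t-test for parametric continuous variables or Mann-Whitney U test for nonparametric or categorical variables", and "P<0.05 will be considered statistically significant for the primary outcome".

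No section says what happens to the sum when a contact is missed. The only replacement rule concerns lost or nonfunctional devices.

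**The concern.** Adding up only the scores that were collected gives the same total as entering 0 for each score that was not. On this scale 0 is a real value, the best possible one. A participant who cannot be reached on one day is therefore recorded as having been free of pain that day. Neither the t-test nor the Mann-Whitney test repairs this, because both take the participant's total as given.

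Two things are at stake. If the arms miss contacts at different rates, the arm that misses more looks better even when the device does nothing. If they miss at the same rate, the absolute difference shrinks and some power is lost. Outpatient scores depend on reaching people by telephone, so some gaps are foreseeable. The Phase II arms also receive different products (active SofPulse, sham RecoveryRx). Equal missingness therefore cannot be taken for granted, although nothing in the documents shows that it will differ.

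The silence also leaves the analyst free to choose between partial sums, exclusion and averaging after the data are seen. Specific Aim 2 uses the estimates to size later trials, so an artefact would be carried forward.

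**Working it through.** **Inputs from the plan.** Sham mean 23.9, SD 12.3, 33% reduction, two-sided alpha 0.05, power 0.80, 1:1 allocation. Phase II total is 70 in the sample-size paragraph, so 35 per arm.

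**The plan's own figure.** Target difference = 0.33 x 23.9 = 7.887 points. Standardized effect = 7.887/12.3 = 0.641. These inputs give 39 per group for 80% power, not the stated 25. With 35 per arm and complete data, power is about 75%. That shortfall is a separate matter; 75% is the baseline below.

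**One missed contact.** On average 23.9/4 = 5.98 points, which is 25% of the sham total and 5.98/7.887 = 76% of the target difference.

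**How many participants are affected.** If contacts are missed independently with probability p, the share with at least one gap is 1 - (1 - p)^4: 19% at p = 5% and 34% at p = 10%.

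**Assumptions for the rest.** The documents give no missing rates, so all rates are assumed. The simulation used four normal day totals with mean shares of 30/27/24/19%, correlation 0.6 and a sum SD of 12.3. Contacts were missing at random, and the mean of available scores required at least 2 contacts. There were 20,000 trials per scenario (4,000 for Mann-Whitney, Monte Carlo error about 0.4 to 0.6 points).

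**No true effect, unequal missingness.** False difference = 23.9 x difference in missing rate. For Day 7 only it is 23.9 x 0.19 x 0.10.

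| Contacts missed | False difference | Share of 7.887 | Type I error, raw sum: t-test | Mann-Whitney |
|---|---|---|---|---|
| 5% vs 2% | 0.72 | 9% | 5.7% | 5.2% |
| 10% vs 5% | 1.20 | 15% | 6.9% | 7.1% |
| 15% vs 5% | 2.39 | 30% | 13.3% | 14.6% |
| Day 7 only, 20% vs 10% | 0.45 | 6% | 5.4% | 5.0% |

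The mean of available scores keeps the t-test at 4.8% to 5.2% in all four rows.

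**True 33% reduction, equal missingness.** Expected difference = 7.887 x (1 - p).

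| Missed | Difference, raw sum | Power, raw sum | Power, mean of available |
|---|---|---|---|
| 5% | 7.5 | 73.0% | 74.8% |
| 10% | 7.1 | 70.6% | 74.0% |
| 15% | 6.7 | 68.1% | 73.5% |

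Both arm means are multiplied by (1 - p), so the percentage reduction stays at 33%.

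**Excluding incomplete participants instead.** There is no false difference under these assumptions. Complete participants per arm fall to 35 x 0.95^4 = 28.5 at 5% missed and 35 x 0.90^4 = 23.0 at 10%. Power falls to 66.1% and 56.0%.

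**Sensitivity to the model.** With day totals held to integers from 0 to 20, raw-sum type I error in the four null rows is 5.6%, 6.8%, 13.6% and 5.3%. Power is 79.6% with complete data and 77.2%, 74.3% and 72.5% at 5%, 10% and 15% missed. The mean of available scores gives 78.6%, 77.9% and 77.6%. A model with gamma-shaped sums and equal day shares also gives about 13% type I error at 15% vs 5%.

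**The case against.** The text does not tell anyone to enter a zero. A careful analyst might set an incomplete sum to missing, and then no false difference arises under the assumptions above. The inflation needs unequal missingness, and the documents offer no evidence of it. Only the assumed 15% vs 5% case is large; two of the four cases stay close to 5%. With equal missingness of 5% the raw sum costs about 2 points of power. There are only four contacts, some may take place in hospital, and the study is described as an exploratory pilot without a data analysis plan.

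Much of this stands. The size is unknown and may be small, and the day shares and correlation are not the plan's. It does not remove the point. The stated rule is to sum what was collected, and followed exactly it gives the partial sum. Exclusion is not written down and costs more power than the raw sum does. The pilot label carries little weight here, because the same section gives Phase II a primary outcome, a power calculation, named tests and a significance threshold. It reserves the weaker, suggestive reading for secondary outcomes.

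**Conclusion.** The concern holds and should be fixed. As written, the Phase II primary score treats a missed contact as no pain, worth about 6 points on average against a 7.89-point target. For assumed gaps between arms of 3 to 10 percentage points across all contacts, the false difference is 0.7 to 2.4 points and the t-test's type I error is 5.7% to 13.3%. For equal missingness of 5% to 15%, power falls from about 75% to between 73% and 68%, while the percentage reduction is unaffected.

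These figures assume that missed contacts carry similar pain in both arms. The power figures also treat 23.9 (12.3) as complete data. If any Phase I sham sum was incomplete, which the documents do not say, the planning values carry the same artefact and part of the shrinkage is counted twice. Confidence in the size is medium, because no missing rate is given.

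**What to change.** In section 9, replace the raw sum with wording such as: *the mean of the available average and worst scores from Days 1, 2, 3 and 7, multiplied by 8; a contact counts only if both scores are recorded, and at least 2 of the 4 contacts are required.* The minimum of 2 is an example; the team should fix one in advance. Requiring both scores gives up an occasional lone score, but average and worst scores differ in level, so a lone one would shift the mean.

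Keep the planned t-test or Mann-Whitney test. Report missed contacts by arm and day, and the number of participants below the minimum. Recompute the Phase I sham mean and SD in the same way. With complete data the new score equals the planned sum, so the standardized effect of 0.64 does not change. A repeated-measures mixed model on the day-level scores is an optional sensitivity analysis.

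**Cost.** One or two sentences and a re-run of the Phase I sham summary; no new data. If contacts are missed independently, a minimum of 2 drops 0.05%, 0.4% or 1.2% of participants at 5%, 10% or 15% missed. A minimum of 3 drops 1.4%, 5.2% or 11.0%.

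**Downside.** The mean ignores which day is missing. If pain falls over the week and only Day 7 is missed (20% vs 10%), the remaining bias is 0.10 x (23.9 x 0.81/3 x 4 - 23.9) = 0.19 points. This runs against the arm that misses more, the opposite direction to the raw sum's 0.45. Nor does the mean remove bias if one arm misses its more painful contacts.

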An analgesic alternative with few associated limitations is **pulsed electromagnetic field (PEMF)** therapy, also called pulsed short-wave therapy, pulsed radiofrequency energy therapy, and radiofrequency nonthermal diathermy.¹ Over the last 7 decades, PEMF has been used to treat acute and chronic pain, decrease inflammation and edema, and hasten wound healing and bone regeneration.¹ Possible mechanisms for the multiple clinical effects of PEMF are multifactorial, complex, and only partially understood.¹ The primary theory involves the promotion of calcium binding to calmodulin which activates endothelial and neuronal nitric oxide synthase isoforms, producing nitric oxide which has anti-inflammatory and analgesic effects, among other consequences

[figure not shown]
such as decreasing edema while increasing blood and lymph flow.¹

[figure not shown]
In 1947, the United States Federal Communications Commission assigned three frequencies for radiofrequency use in medical treatments: 40.68, 13.56 and 27.12 MHz.¹ Within just a few years, the first pulsed electromagnetic field generator was cleared by the United States Food and Drug Administration for use with patients using 27.12 MHz: the Diapulse.^{2,3}. Until relatively recently, available devices consisted of a large signal generator and bulky coil applicator that were not portable and produced significant electromagnetic interference, making them impractical for common use (Figure, right). However, over the past 70 years they have exhibited an extraordinary safety profile: these are noninvasive, nonpharmacologic devices, with no side effects, adverse events, or medication interactions; and the only

contraindications are pregnancy and an implanted pulse generator such as a cardiac pacemaker. Unlike opioids, there is no risk of abuse, dependence, and/or diversion.

More recently, small, simple, lightweight, battery-powered, noninvasive PEMF devices have received FDA clearance for use treating acute and chronic pain, including the ActiPatch and RecoveryRx for amputees and the initial 150 surgical subjects of Phase I (Model 088, BioElectronics, Frederick, Maryland; **Figure, below left**); as well as SofPulse for the subsequent 80 surgical subjects of Phase II (Endonovo Therapeutics, Woodland Hills, California; **Figure below right**). We will be using the devices for FDA-approved indications; in other words, on-label use.

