9. RESEARCH DESIGN AND METHODS

This will be a single-center (UCSD), randomized, participant- and observer-masked, sham-controlled, parallel-arm human subjects pilot study.

Enrollment. Participants will be consenting adults either (1) undergoing various surgical procedures usually resulting in moderate-to-severe postoperative pain, or (2) experience post-amputation phantom and/or residual limb pain. Study inclusion will be proposed (1) to eligible presurgical patients or (2) after an amputee contacts the investigators. If an individual desires study participation, written, informed consent will be obtained using a current UCSD IRB-approved ICF. The study population of interest includes adult women and men of all races, ethnicity, sexual identity, and socioeconomic status. Inclusion and exclusion criteria are listed in section #10 below.

Procedures. Following written, informed consent, we will record baseline anthropometric information (age, sex, height, weight, amputation details and current pain levels). Surgical participants will receive any standard peripheral nerve block(s) administered using bupivacaine or ropivacaine 0.5% with epinephrine (standard at UCSD) prior to undergoing their surgical procedure *per standard of care*.

Treatment Group Assignment. Each participant will be randomized to one of two treatment groups: *Active* or *Sham* treatment. For the initial 150 subjects of Phase I, there are sham RecoveryRx devices produced that are identical to active RecoveryRx devices, only they do not deliver PEMF. Randomization will be stratified by surgical procedure/amputation, in block sizes of 2. The computer-generated randomization lists will be created by the University of California San Diego Investigational Drug Service in a 1:1 treatment group ratio using opaque envelopes. For the initial 150 subjects of Phase I using RecoveryRx devices, the active and sham devices are indistinguishable in appearance, and therefore investigators, participants, and all clinical staff other than the individual who opens the randomization envelope and chooses a sham or active device will be masked to treatment group assignment for the duration of the data collection period. For the subsequent 80

subjects of Phase II, active SofPulse devices will be provided to patients randomized to the active treatment group; and sham RecoveryRx devices will be provided to the patients randomized to the sham treatment group.

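### The Phase II sample size does not follow from its own inputs: they need 39 to 40 per group, not 25, and the planned 70 give about 75% power with no margin

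*Combined protocol and SAP*

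**What the plan says.** The Phase II sample size is in Section 9 (Research Design and Methods), after the description of end points. Phase II is to be analysed separately from Phase I. Its primary outcome is each participant's sum of the average and worst daily pain scores collected in the first 7 postoperative days.

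The effect to detect is set by "We will consider a 33% reduction in pain scores to be the minimal clinically important difference". The sham mean (SD) of 23.9 (12.3) is taken from Phase I sham patients. The result is "Assuming a two-sided type I error protection of 0.05 and a power of 0.80, approximately 25 patients in each group are required", credited to an online calculator. The enrolment target follows: "To allow for a higher degree of variability than anticipated we will enroll a total of 70 participants in Phase II", made up of 30 cholecystectomy and 40 hip or knee arthroplasty patients.

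The analysis text names Student's t-test, or Mann-Whitney if the data are not parametric, and sets P<0.05 for the primary outcome. Allocation is "in a 1:1 treatment group ratio using opaque envelopes".

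Elsewhere the Phase II total is different. Section 7 (Background and Significance) has "SofPulse for the subsequent 80 surgical subjects of Phase II", and the treatment group assignment text in Section 9 also says 80.

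**The concern.** A 33% reduction from 23.9 is about 7.9 points, or roughly 0.64 of the stated SD. A standardised difference of that size needs close to 40 per group for 80% power at two-sided 0.05, so 25 looks far too low. If so, the step from 50 to 70 is not a safety margin: 70 would itself be short of the correct requirement.

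Phase II has its own hypothesis, primary outcome, stated power and significance threshold, and it cannot borrow Phase I data. A reader who trusts the stated power would take a null result as reasonable evidence against a 33% reduction when the trial was less able to show one than claimed. The results are also meant to inform later definitive trials.

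**Working it through.** **Inputs (all from Section 9)**

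- Sham mean 23.9, SD 12.3. No active-group SD is given, so a common SD is assumed.
- Difference: 0.33 × 23.9 = 7.887 points.
- Standardised difference: d = 7.887 / 12.3 = 0.641.
- Two-sided alpha 0.05, power 0.80, 1:1 allocation, two-sample t-test.

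**Required number per group**

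n = 2 × (1.960 + 0.8416)² × SD² / difference² = 2 × 7.849 × 151.29 / 62.205 = 38.2, so 39. Solving with the noncentral t distribution gives 39.2, so 40. (At 39 per group the t-test power is 79.8%.) Reading 33% as exactly one third (7.967 points) gives 37.4, so 38, by the formula and 38.4, so 39, by the t-test.

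**Attempts to reproduce 25**

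| Variant | n per group |
|---|---|
| As stated, normal formula | 39 |
| As stated, t-test | 40 |
| One-sided alpha 0.05 | 31 |
| One-sample formula | 20 |
| Mann-Whitney (39.16 / 0.955 = 41.01) | 42 |
| Active SD shrinking with its mean (0.67 × 12.3 = 8.24) | 28 (t-test 29) |
| The same, one-sided | 22 |
| Log scale, constant coefficient of variation | 23 |

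None gives 25. The log-scale version comes within 2 patients, but the plan states no transformation and describes a t-test on the summed score. Working backwards with the t-test, 25 per group gives 80% power for a 9.95-point (41.6%) reduction at SD 12.3, or for a 33% reduction if the SD is about 9.75.

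**Power of the stated numbers**

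Two-sample t-test, noncentrality d × √(n/2), 2n − 2 degrees of freedom:

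| Per group | Total | Noncentrality | Power |
|---|---|---|---|
| 25 | 50 | 2.267 | 60.3% |
| 35 | 70 | 2.682 | 75.3% |
| 40 | 80 | 2.868 | 80.8% |

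**Is there a margin at 70?**

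- With 35 per group, 80% power requires d = 0.679. That is a difference of 0.679 × 12.3 = 8.36 points (8.36 / 23.9 = 35.0%), or an SD of at most 7.887 / 0.679 = 11.6.
- The ceiling of 11.6 is already below the anticipated 12.3.
- If the SD is 15% higher (1.15 × 12.3 = 14.1), which is the kind of event the margin is meant to cover, power at 70 falls to about 63%.

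These figures assume that every enrolled participant contributes the outcome. The sample size text has no dropout allowance.

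**The case against.** The strongest reply is that the plan gives an SD for the sham group only. If the active group's SD fell in proportion to its mean, to 8.24, the t-test requirement would be about 29 per group. In that case 70 would give about 87% power, and still 77% if both SDs were 15% larger. This stands as a qualification: the 75% figure depends on equal SDs. It does not defend the text. One quoted SD is conventionally read as common to both groups, the plan states no other assumption, and 29 is still not 25. For 70 to reach 80% with a sham SD of 12.3, the active SD would have to be no more than √(2 × 11.61² − 12.3²) = 10.9.

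A second reply is that the operative loss is modest. The trial enrolls 70, not 50, so the shortfall is about 5 percentage points, and it disappears if the real target is 80. That is fair, and the 60% figure describes a trial nobody plans to run. The errors that remain are the stated requirement and the claim of spare capacity.

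A third reply is that this is a pilot, and that the plan describes the study as exploratory. No passage says that a null result would be treated as definitive. But Section 9 gives Phase II a powered hypothesis test at P<0.05 and treats only the secondary outcomes as merely suggestive, so the stated power should be correct.

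**Conclusion.** The concern holds. The stated inputs require 39 per group (40 by the t-test), so the published 25 is 14 to 15 per group too low. "Approximately" cannot cover that gap, and no method described in the plan closes it.

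Under a common SD of 12.3 with complete data, the planned 70 give about 75% power for a 33% reduction, or 80% power for a 35% reduction. The assertion that 70 absorbs extra variability is therefore unsupported.

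The failure to reproduce 25 does not depend on the equal-SD assumption; the shortfall at 70 does. Because 70 and 80 lie on opposite sides of the 80% line, the conflict between the totals decides whether the stated power is met.

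**What to change.** In Section 9:

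1. Replace 25 per group with 39 to 40, and state the SD assumed for the active group and the calculator inputs.
2. Settle the Phase II total and use it in both places in Section 9 and in Section 7.
   - If it is 70, say that this gives about 75% power for a 33% reduction, or 80% for a 35% (8.4-point) reduction, under a common SD of 12.3.
   - If it is 80, say that this gives about 81%, and revise the procedure split, which now sums to 70 (30 + 40).
3. Delete the statement that the total allows for more variability than expected. Neither total offers a material margin under a common SD.

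Keeping 70 costs wording only, with a slightly less favourable stated power. Choosing 80 means 10 more participants than the sample size text, though that number already appears elsewhere in the plan. With 150 Phase I surgical participants it makes 230, which leaves 40 of the 270 maximum in Section 10 for amputees and anyone else who signs consent.

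### The Phase II primary comparison of summed 7-day pain is unadjusted, although preoperative pain appears to be recorded and procedure is a randomization stratum: a loss of precision, not an error

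*Combined protocol and SAP*

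**What the plan says.** All references are to the combined protocol and SAP.

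- **Primary outcome (section 9, Phase II paragraphs).** The outcome is defined thus: "for each participant all of the 'average' and 'worst' daily pain scores collected within the first 7 postoperative days will be summed". It is tested at P<0.05.
- **Test (section 9, last paragraph).** "Comparisons of independent samples will be performed using Student's t-test for parametric continuous variables", with Mann-Whitney U for nonparametric or categorical variables. No regression model, covariate or stratified analysis is named.
- **Baseline data (section 9, Procedures).** After consent, "we will record baseline anthropometric information (age, sex, height, weight, amputation details and current pain levels". The sentence is not limited to amputees, and the one after it turns explicitly to surgical participants.
- **Scale (section 9, Outcome measurements).** "All pain scores will be measured using the Numeric Rating Scale (0: no pain, 10: worst imaginable pain".
- **Timing (section 12).** Surgical participants arrive 15 minutes early for consent and collection of baseline information. The content of that information is not listed.
- **Assessment table (section 9).** Pain has a Day 0 column for amputees. The surgical columns begin at postoperative day 1.
- **Randomization (section 9).** Allocation is 1:1, stratified by procedure, in blocks of 2. Phase II comprises 30 cholecystectomies and 40 hip or knee arthroplasties.

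**The concern.** Preoperative pain, if recorded, is on the same 0-10 scale as the scores summed for the outcome, and is known before the device is applied. Procedure is known for every participant and was judged important enough to stratify on. Either may explain part of the variation between patients behind the planning SD of 12.3. A two-sample test leaves that variation in the error term.

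Two things are at stake. First, the confidence interval may be wider, and power lower, than the same 70 patients would allow. Second, the design balances procedure but not preoperative pain. With 35 per arm, a chance difference in preoperative pain would pass into the unadjusted estimate in proportion to rho. Section 6 makes estimating the treatment effect, to size later trials, one of the two aims, so precision matters here beyond the significance test.

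**Working it through.** **Inputs from section 9.** The target effect: "We will consider a 33% reduction in pain scores to be the minimal clinically important difference". The planning values for the sham arm are mean 23.9 and SD 12.3; alpha is 0.05, two-sided, and target power is 80%. Enrolment is 70 at 1:1, so 35 per arm.

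**1. The plan's own figure.** Target difference: 0.33 × 23.9 = 7.887 points. Standardized: 7.887 / 12.3 = 0.641. Normal-approximation sample size per arm:

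n = 2 × [(1.960 + 0.842) × 12.3 / 7.887]² = 38.2, so 39.

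The t-test version gives 39.2, so 40. The stated 25 per group is not reproduced. That is a separate matter; it is relevant here only because it leaves 70 participants a little short of 80% power.

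**2. Power of the planned test.** Noncentral t with 68 degrees of freedom and noncentrality 0.641 × √(35/2) = 2.682: power 75.3%.

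**3. Power with the baseline covariate.** If rho is the within-arm correlation between preoperative NRS and the 7-day sum, the residual SD is 12.3 × √(1 − rho²), with one degree of freedom fewer (67). The document gives no rho, so a range is shown. The CI half-width is 1.96 × residual SD × √(2/35).

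| rho (assumed) | Variance removed | Residual SD | Power, 35 per arm | 95% CI half-width |
|---|---|---|---|---|
| Unadjusted | – | 12.30 | 75.3% | 5.76 |
| 0.1 | 1% | 12.24 | 75.7% | 5.73 |
| 0.2 | 4% | 12.05 | 77.0% | 5.65 |
| 0.3 | 9% | 11.73 | 79.1% | 5.50 |
| 0.4 | 16% | 11.27 | 82.2% | 5.28 |

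At rho 0 the adjusted power is still 75.3% to one decimal. A further one or two degrees of freedom for procedure change the powers shown by less than 0.1 point.

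**4. Procedure.** With fractions 30/70 and 40/70, a difference D between procedure means contributes variance (30/70)(40/70)D². No D is given. For assumed values of 5, 8 and 10 points, the share of 12.3² is about 4%, 10% and 16%. This overlaps with step 3 if preoperative pain differs by procedure, so the two gains must not be added.

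**5. Chance imbalance.** The standardized baseline difference between arms has SD √(2/35) = 0.239. A one-SD imbalance shifts the unadjusted estimate by 0.239 × rho × 12.3: 0.59 points at rho 0.2 and 0.88 at rho 0.3, against the 7.89-point target.

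**The case against.** **The baseline value may not exist for surgical patients.** Current pain is listed directly after amputation details, the table gives Day 0 pain to amputees only, and only the amputee outcome is defined as a change from baseline. This stands in part. The table is captioned as post-enrollment assessments and its surgical columns are postoperative days, so a preoperative value need not appear there. The Procedures sentence covers all who consent, and section 12 confirms some baseline collection before surgery. A reader might infer that a value certainly in hand is being discarded; the document does not support that.

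**The correlation may be weak.** Section 10 sets no pain threshold for surgical patients and excludes chronic opioid users. Surgery and any nerve block fall between the two measurements, and a single current rating would predict a sum of average and worst scores. This stands. A reader might assume a correlation such as 0.5, which would give 86.3% power, but nothing in the document supports that value. At 0.1 to 0.2 the gain is under 2 points.

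**Procedure is the better-documented covariate.** This stands, and the model should include it.

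**This is an exploratory pilot and the test is valid.** Validity is conceded, and the unadjusted interval already allows for chance imbalance on average. Pilot status does not settle the matter: Phase II has a powered primary comparison with a significance threshold.

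**More patients would do the same work.** Other parts of the protocol give 80 Phase II subjects; at 40 per arm the unadjusted power is 80.8%. But the Phase II sample-size text says 70, and adjustment needs no extra patients.

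**Conclusion.** The point holds as one of efficiency. The only tests named for the Phase II primary outcome are unadjusted, and no covariate is used anywhere. A reader might conclude that the primary analysis is wrong or biased; the document does not support that, since randomization makes the unadjusted comparison valid.

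The size of the gain is not known. With 35 per arm and the plan's difference and SD, it is 0.4 points of power at rho 0.1, 1.7 at 0.2, 3.8 at 0.3 and 6.9 at 0.4, from a base of 75.3%. These figures assume a linear relation, the same correlation in both arms, a planning SD of 12.3, complete baseline data, and no overlap between preoperative pain and procedure. Overlap would make the gain over a procedure-adjusted model smaller. Because almost nothing is lost if rho is near zero, prespecifying the adjustment is worthwhile despite the uncertainty.

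**What to change.** **Section 9, Phase II analysis.** Before unblinding, state that the summed 7-day pain score will be compared by a linear model (ANCOVA) with treatment, surgical procedure (as stratified at randomization) and preoperative NRS. Report the adjusted mean difference with a 95% CI. Keep the unadjusted test as a sensitivity analysis. State how a missing preoperative score will be handled.

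**Section 9, Procedures.** State that current pain is recorded on the NRS, before surgery, for surgical participants.

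**Cost.** A few sentences and a few degrees of freedom; no extra patients or visits. If preoperative pain has not been recorded in surgical patients, add one NRS question at the existing pre-surgery consent visit. Anyone already enrolled in Phase II would then lack the covariate; the procedure term would still be available for them.
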